10 ANALYSIS POPULATIONS

10.1 Screened Population

The screened population consists of all the subjects who give informed consent.

10.2 Safety Population

The safety population, consists of all the subjects who signed informed consent, have at least one exposure to P3P (including the product test at Admission [Day -1]) and have at least one safety assessment.

10.3 Randomized Population

The randomized population is a subset of the safety population and consists of all randomized subjects who had at least one post-randomization P3P exposure and have at least one valid non-safety assessment.

10.4 PK Population

The PK population is a subset of the randomized population and consists of all subjects who completed at least one of the single use of P3P for PK assessment, and for whom at least one primary nicotine PK parameter can be derived. Only subjects without major protocol deviations that impact evaluability of the data (see Section 11 “Protocol Deviations”) will be included in the PK analysis sets.

11 PROTOCOL DEVIATIONS

Protocol deviations are defined as deviations from the study procedures, including but not limited to any violation of inclusion/exclusion criteria, assessments not performed or performed outside the scheduled time windows, or use of drugs that are known to affect study endpoints.

All protocol deviations will be entered into the clinical trial management system (CTMS) or other approved format.

All deviations will be reviewed and each deviation will be classified as major or minor; all major deviations will be further reviewed to determine whether or not the deviation impacts the evaluability of the subject for the primary objectives of the study and therefore should result in the subject being excluded from the primary analysis population.

11.1 Major Protocol Deviations

Subjects with major protocol deviations will be identified (at a population level) to determine whether they will be excluded from any of the analysis populations. The following have been identified as the major protocol deviations.

The categories for the major deviations will include, but are not limited to the deviations presented in Table 9.

Table 9: Definition of Major Protocol Deviations

Category	Description
Violation	Violation of inclusion/exclusion criteria (see below table)
Mis-randomization	Being administered the wrong product according to the randomization schedule during the entire exposure period
Mis-use of product (PK)	
Use of any nicotine or tobacco-containing product during the wash-out periods.Inadequate use of P3P product for PK assessment on D1 or D30 (eg. Product not used at all, product not pierced,...)
Concomitant medication	Medications within 5 half-lives of the drug prior to D1 or D30 with an impact on CYP2A6 activity
Visit missing	Subject did not attend a scheduled visit
GCP Deviation	Samples being analyzed in spite of written withdrawal of consent for analysis
Reporting of product use	Less than 75% of the daily product use reported in the e-diary over a period is available, or daily product use not reported over a period of more than 7 consecutive days

Violation of exclusion criteria 11 (Subject has received medication within 14 days or within 5 half-lives of the drug prior to Admission (whichever is longer) which has an impact on CYP2A6 activity) will be considered as preventing the evaluation of the primary objective. Such deviations will be considered as major and rendering the subject data non-evaluable for the primary objective.

Among the eligibility criteria, violations of inclusion criteria 2, 3 and 4, or of the exclusion criteria 10 will be assessed for their impact on the evaluability of the primary objectives during the pre-analysis data review meeting.

11.2 Minor Protocol Deviations

The categories for the minor deviations will include, but are not limited to the deviations presented in Table 10.

**Table 10: Definition of Protocol Deviation Categories**

Category	Description
Time deviation (Plasma nicotine PK sample)	Assessments not taken at the correct time or within the allowed time window or date/time is missing (see Table 11: Definition of Assessment Windows).
Time deviation (other assessments)	Assessments not taken at the correct time or within the allowed time window or date/time is missing (see Table 11: Definition of Assessment Windows)
Assessment missing (Plasma nicotine PK sample)	PK Assessment is missing
Assessment missing (other assessment)	Assessment is missing
Procedural violation	Violation of planned procedure
Mis-use of product (other)	Use of the wrong P3P variant for a limited period; use of more than 15 P3P products on a single day

11.2.1 Assessment Windows

On Day 1 (V2) and Day 30 (V6), after at least 10 hour abstinence from any tobacco/nicotine containing products, subjects will use a single P3P product, as randomized, for a duration of up to 15 minutes. The start of product use (first puff taken) will be defined as T_0 .

The windows reported in Table 11: Definition of Assessment Windows will be applied to the timing of data collection.

Table 11: Definition of Assessment Windows

Assessment	Nominal Time point(s) (relative to T_0)		Window
Plasma nicotine	Baseline		
PK sample	1hr , 30 min prior T_0	± 5 minutes	
	5 min	± 2 minutes	
	Post Baseline (post T_0)		
	4, 7, and 10 min	± 1 min	
	15, and 30 min	± 2 min	
	1, 2, and 4h	± 5 min	
VAS	Baseline		
	10 min prior T_0	± 2 minutes	
	Post Baseline (post T_0)		
	4, 10, and 15 min	± 2 min	
	30 min	± 5 min	
	1, 2, and 4h	± 10 min	

Subjects will return to the investigational site for weekly visits, V3 (Day 7), V4 (Day 15), V5 (Day 22) and V6 (Day 29) with a visit time window of \pm 2 days each. The visit days and windows will be calculated from Day 1.

12 PLANNED STATISTICAL METHODS

12.1 General Considerations

Data analysis will be performed using SAS[®] Version 9.3 or higher.

Data listings will be provided for all data collected, ordered by P3P variant and subject, unless otherwise stated. Summary statistics and statistical analysis will only be presented for data where detailed in this SAP. All unscheduled assessments will be included in the listings only.

12.1.1 Stratified Presentation

Data summaries will be produced by P3P variant and time point (if applicable), unless otherwise stated.

Stratified presentations by sex and product exposure category will be conducted on the randomized population for the following endpoints:

- Demographics and baseline characteristics
- VAS craving, Sensory questionnaire, and ABOUTTM-Product Experience questionnaire
- Product acceptance questionnaire
- Biomarkers to HPHCs (NEQ, CEMA, and total NNAL)
- Puffing/inhalation behavior (only by product exposure category)
- ABOUTTM-Dependence questionnaire (only by product exposure)
- CYP2A6

Stratified presentations by actual product exposure category will be conducted on the PK population for the following endpoints:

- Demographics and baseline characteristics
- PK parameters
- Weight difference of P3P

Stratified presentations by sex will be conducted on the PK population for the following endpoints:

- PK parameters

Stratified presentations by actual product exposure category will be conducted on the Safety population for the following endpoints:

- Demographics and baseline characteristics
- Cough assessment
- ECG
- Vital Signs
- Spirometry

12.1.2 Subgroup Analyses

No subgroup analyses are planned.

12.1.3 Descriptive Statistics

All data will be presented in listings.

All endpoints will be summarized with descriptive statistics including number of subjects (n), number and percent of subjects with missing data, arithmetic means, 95% confidence intervals of the mean, and standard deviations (SD), median, first and third quartiles, minimum and maximum. Change from baseline will be added to the summary statistics when applicable.

For log normally distributed endpoints geometric mean, 95% confidence intervals of the geometric mean, geometric CV will be presented instead of arithmetic mean, 95% confidence intervals of the mean, and SD and percent change from baseline will be presented instead of change from baseline.

Categorical variables will be summarized by frequency statistics (number and percentage). For endpoints relating to sampling times (e.g., tmax) only median, first and third quartiles, and minimum and maximum will be presented.

Summary statistics and statistical analyses will be performed for subjects included in the relevant analysis population. For the calculation of summary statistics and statistical analysis, unrounded data will be used.

Summaries on Safety population will be produced by randomization group and overall, including the available data from subjects who tested the product but were not randomized.

The following product labels and descriptions will be used for the TFLs (Table 12):

Table 12: Product Labels

Randomization Group/P3P Variant	Format used in TFLs	Order in TFLs
P3P-1mg	P3P-1mg	1

P3P-2mgP3P-2mg

2

The following stratification labels (Table 13) for the TFLs will be used:

Table 13: Stratification Labels

Stratification Factor	
Sex	Male
	Female
Product Exposure Category	≤ 5 P3P/Day
	>5-10 P3P/Day
	>10 P3P/Day

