### 12.3 Analysis Populations

Pharmacokinetic, pharmacodynamics, product acceptance, puffing/inhalation behavior endpoints will be analyzed using the PK population by actual product exposure and overall. Nicotine/tobacco containing product use, tobacco and nicotine containing product dependence, and CYP2A6 activity will be analyzed using the randomized population by actual product exposure and overall. Exposure to harmful and potentially harmful constituents will be analyzed using the randomized population. Safety will be analyzed using the safety population by actual product exposure and overall.

Actual product use exposure categories will be further defined in the SAP. Additional populations for sensitivity analysis could be defined in the SAP.

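### Safety summaries are grouped by randomization group, so a randomized subject who receives the other variant throughout would have post-randomization safety data reported under a nicotine content not used.

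*SAP*

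**What the plan says.** SAP 12.1.3 gives the grouping rule for the Safety population: "Summaries on Safety population will be produced by randomization group and overall". The sentence goes on to bring in subjects who tried the product on Day -1 but were never randomized. Table 12, directly below, heads its column "Randomization Group/P3P Variant", so assigned group and variant share one label. SAP 12.5.9 and 12.5.9.2 later say that safety and adverse event tables are presented by variant and overall. They do not say whether that means the variant assigned or the variant used.

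SAP 10.2 admits consenting subjects who "have at least one exposure to P3P (including the product test at Admission [Day -1]) and have at least one safety assessment". It contains no exclusion for protocol deviations.

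SAP 11 foresees that assigned and used variant may differ. Table 9, under mis-randomization, lists as major "Being administered the wrong product according to the randomization schedule during the entire exposure period". Table 10 lists as minor "Use of the wrong P3P variant for a limited period". SAP 11.1 says that subjects with major deviations will be identified "to determine whether they will be excluded from any of the analysis populations".

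**The concern.** The two variants differ in nicotine content, 1 mg against 2 mg per product (Protocol 6.1.1). A side-by-side safety table is read as showing what happened to people using each of them. Under the stated rule, a subject who used one variant from Day 1 onward can be counted under the other. This would affect the adverse event and serious adverse event tables and the laboratory, ECG, vital sign and spirometry summaries alike.

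The SAP provides a route for such a subject in the PK analysis, because SAP 10.4 removes major deviations that affect evaluability. It provides no matching rule for safety. With about 30 subjects per arm, one misplaced subject can be visible in an adverse event row.

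**Working it through.** The plan states no figure that depends on the grouping rule. The sample size is empirical, with no power, effect size or standard deviation (SAP 8). The check is therefore a reading of the text followed by a simple count.

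**Reading the rules together**

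1. SAP 12.1.3 sets the grouping as randomization group, and Table 12 equates that with variant. The later references to variant therefore do not switch the tables to the variant used.
2. Table 9 names a case in which assigned and used variant differ for the whole exposure period.
3. SAP 10.2 keeps that subject in the Safety population.
4. No section of the SAP moves the subject to the column of the variant received.
5. The presentations by product exposure category do not fill the gap. SAP Table 7 and 12.1.7 define the categories by average number of products per day (up to 5, more than 5 to 10, more than 10) within variant. For the Safety population, SAP 12.1.1 lists them only for demographics, cough, ECG, vital signs and spirometry. Adverse events and laboratory data are not on that list.

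**Size**

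The one input from the plan is 60 randomized at 1:1, about 30 per arm (SAP 8). One subject is 1/30 = 3.3% of an arm. The numbers of deviating subjects and of events below are assumptions for illustration.

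Suppose *m* subjects are randomized to P3P-1mg, use P3P-2mg throughout, and each has an event that nobody else has. By randomization group the rates are *m*/30 against 0/30. By variant received they are 0/(30 − *m*) against *m*/(30 + *m*).

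| *m* | By randomization group, 1 mg vs 2 mg | By variant received, 1 mg vs 2 mg |
|---|---|---|
| 1 | 1/30 (3.3%) vs 0/30 (0%) | 0/29 (0%) vs 1/31 (3.2%) |
| 2 | 2/30 (6.7%) vs 0/30 (0%) | 0/28 (0%) vs 2/32 (6.2%) |
| 3 | 3/30 (10.0%) vs 0/30 (0%) | 0/27 (0%) vs 3/33 (9.1%) |

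**Direction**

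Take assumed counts by randomization group of 3/30 (10.0%) against 5/30 (16.7%), a difference of 6.7 percentage points. Move one subject from the 1 mg to the 2 mg column.

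- If that subject had the event: 2/29 (6.9%) against 6/31 (19.4%), a difference of 12.5 points.
- If that subject did not: 3/29 (10.3%) against 5/31 (16.1%), a difference of 5.8 points.

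So grouping by assignment understates the difference in the first case and overstates it in the second.

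**The case against.** The strongest reply is that this is loose wording, not a deliberate choice of an as-randomized safety analysis. The sentence in SAP 12.1.3 mainly sets the columns and brings in product-test-only subjects, and the SAP uses randomization group and variant interchangeably. That may well be the history, but a programmer who follows the text would still use the assigned group.

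A second reply is that case review before lock could deal with the subject. SAP 11.1 does allow that. However, SAP 10.2 gives no ground for exclusion, and exclusion would discard the safety data instead of placing it correctly.

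A third reply is that the harm is hypothetical. Table 9 is a list of categories, not a forecast. Allocation is by IWRS at one center, dispensing is logged, the study is descriptive, and full data and deviation listings would keep the subject traceable. All of this stands, and it limits the weight of the point.

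Three stronger readings are tempting, and the documents do not support them.

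- **A conflict with the protocol.** Protocol 12.3 says "Safety will be analyzed using the safety population by actual product exposure and overall", which a reader might take as grouping by variant received. The same phrase is applied there to PK, product use and other endpoints, and the section continues: "Actual product use exposure categories will be further defined in the SAP". The SAP then defines those categories by products per day. Consumption intensity is the natural meaning, so neither a contradiction nor an undeclared change in SAP 9 is shown.
- **Misplacement of all the subject's safety data.** Every randomized subject must try at least one product of each variant on Day -1 (SAP 6.1), and adverse events after product-test use enter the summary tables (SAP 12.5.9.1). Those early events belong to neither variant alone under either grouping. The point is confined to data after randomization.
- **Dilution of the contrast.** A reader might expect misplacement to pull the two variants together. With one or two subjects it can go either way, as the count shows.

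**Conclusion.** The point holds in a limited form. Followed as written, SAP 12.1.3 would report a wrong-variant subject's post-randomization safety data under a nicotine content that the subject did not use, and no other section corrects this. Each such subject is about 3.3% of an arm. In the illustration with a unique event, one subject moves roughly 3 percentage points of incidence from one column to the other.

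This rests on the SAP being applied literally, on about 30 randomized subjects per arm, and on the deviation actually occurring. Its frequency is unknown. If it does not occur, nothing changes, and the overall column is unaffected in any case. The point concerns attribution of safety data, not PK evaluability. It is a low-priority improvement.

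**What to change.** State in SAP 10.2 and 12.1.3 that randomized subjects in Safety-population summaries are grouped by the variant actually received after randomization, plus an overall column. Show subjects who only took part in the product test separately or in the overall column only, since they have no randomized variant. Flag every wrong-variant or mixed-use subject in the safety listings.

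Mixed use (the Table 10 case) needs its own rule, written down before database lock. Candidates include the variant used on most exposure days, or the variant in use when an event began. The documents do not favor either, so the sponsor should choose one and record it.

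The cost is a sentence in two sections, one derived flag for the variant received, and agreement on the mixed-use rule. A reassigned subject no longer sits in the randomized group, which is acceptable for descriptive safety tables. If no such deviation occurs, the variant columns for randomized subjects are identical to those now planned.

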12.1.4 Definitions of Baseline for Statistical Data Analysis

Baseline values for pharmacodynamic parameters (VAS Craving, Sensory Questionnaire, ABOUT™-Product experience), Product Acceptance, ABOUT™-Dependence, and Puffing/Inhalation behavior questions are defined in section 7.1, 7.2.1, 7.2.2, 7.2.3, 7.3.1, 7.5.1 and 7.3.2 respectively.

Baseline values of BoExp will be defined as the value measured on V2 (Day -1) when spot urine should be collected prior to product test. Baseline for CYP2A6 will be defined as the value determined on Day 1, see section 7.6.

For safety parameters the last assessment prior to product test at Day -1 will be considered as baseline.

12.1.5 Handling of Unplanned Data

Unscheduled post-product use assessments will be excluded from the summary statistics. Unscheduled assessments will be labelled as unscheduled in the listings and mapped to the study day using the date of the study day until midnight.

12.1.6 Multiple Comparisons / Multiplicity

No formal adjustment of the test-wise alpha level for multiple testing is necessary, as no claim will be made based on the outcome of the individual CI values.

12.1.7 Definitions of Product Exposure Categories

Product exposure categories will be created by calculating the average P3P consumption over the exposure period (from Day 1 to Day 29) as the total number of P3P consumables used during the exposure period / duration of the exposure period.

Subjects will be categorized according to their average P3P consumption in one of the 3 product exposure categories by variant (total of 6 subgroups):

- ≤ 5 P3P/Day

- >5-10 P3P/Day
- >10 P3P/Day

12.2 Disposition of Subjects

The number and percent of subjects will be summarized for the following categories: subjects screened, screening failed, enrolled subjects, enrolled and not randomized, randomized subjects, completed, and discontinued.

Reasons for screen failure will be summarized in the screened population.

All subjects who fail to complete the study will be categorized by their primary reason for discontinuation and summarized by P3P variant and overall. Disposition of subjects and reasons for withdrawal will also be summarized separately. Supportive listings will be provided.

The number and percent of randomized subjects with protocol deviations and the number of protocol deviations will be summarized by P3P variant and overall, broken down by main deviation category (major/minor) and sub-categories in the randomized population. Subjects will be counted once per deviation category, and can be counted for more than one deviation category.

Supportive listing will be provided, including any additional comments for tests that are not performed to be included on the listings of individual data.

The data will be presented in the below outputs:

TFL number	Title
TABLES	
15.2.1.1	Reason for Screen Failure – Screened Population
15.2.2.1	Summary of Subject Disposition – Safety Population
15.2.2.2	Summary of Reasons for Discontinuations – Randomized Population
15.2.3.1	Summary of Protocol Deviations – Randomized Population
LISTINGS	
15.1.1.1	Listing of Inclusion/Exclusion Criteria – Screened Population
15.1.2.1	Listing of Subject Disposition and Assignment to Analysis Sets – Randomized Population
15.1.3.1	Listing of Protocol Deviations – Randomized Population
15.1.3.2	Listing of Subjects and Observations Excluded from the PK Population and PK Analysis – Randomized Population
16.1.1	Listing of Randomization Scheme and Codes

12.3 Demographics and Other Baseline Characteristics

Demographic and baseline characteristics will be summarized for the Safety, Randomized and PK populations, and listed for the Safety population.

The demographic variables age, sex, ethnicity, and BMI will be summarized by P3P variant and overall.

Demographics will be tabulated overall, by the sex stratification factor, and by product exposure category as specified in Section 12.1.1 “Stratified Presentation”.

No inferential analyses will be presented for the demographic and baseline characteristics.

The data will be presented in the below outputs:

TFL number	Title
TABLES	
15.2.4.1	Summary of Demographics and Other Baseline Characteristics – Safety Population
15.2.4.2	Summary of Demographics and Other Baseline Characteristics – Randomized Population
15.2.4.3	Summary of Demographics and Other Baseline Characteristics – PK Population
15.2.4.4	Summary of Demographics and Other Baseline Characteristics By Sex – Safety Population
15.2.4.5	Summary of Demographics and Other Baseline Characteristics By Sex – Randomized Population
15.2.4.6	Summary of Demographics and Other Baseline Characteristics By Sex – PK Population
15.2.4.7	Summary of Demographics and Other Baseline Characteristics By Product Exposure Category – Safety Population
15.2.4.8	Summary of Demographics and Other Baseline Characteristics By Product Exposure Category – Randomized Population
15.2.4.9	Summary of Demographics and Other Baseline Characteristics By Product Exposure Category – PK Population
LISTINGS	
15.1.4.1	Listing of Demographics – Randomized Population

12.3.1 Medical History and Concomitant Diseases

Medical history is defined as any condition that started and ended prior to the ICF signature at V1. Medical history will be coded using Medical Dictionary for Regulatory Activities (MedDRA) version 22.0 and listed separately by P3P variant, System Organ Class (SOC) and Preferred Term (PT) within SOC.

A concomitant disease is defined as any condition that is either detected or is still ongoing at the time of ICF signature Concomitant disease will be coded using MedDRA version 22.0 and listed separately by P3P variant, SOC and PT within SOC.

Partial dates will not be imputed, but assumptions will be made as follows to assign to either medical history or concomitant diseases:

Date information	Assign as
Missing stop date	Concomitant disease
Partial date, e.g., --May2019, or -----2011. If month/year is the same as, or later than the month and/or year of Screening.	Concomitant disease
Partial date, e.g., --May2019, or -----2019. If month and/or year is earlier than the month and/or year of Screening.	Medical history

The data will be presented in the below outputs:

TFL number	Title
TABLES	
15.2.5.1	Summary of Medical History – Safety Population
15.2.6.1	Summary of Concomitant Diseases – Safety Population
LISTINGS	
15.1.5.1	Listing of Medical History – Safety Population
15.1.6.1	Listing of Concomitant Disease– Safety Population

